#### 9.4.2.1.1 Adverse events

Adverse events will be coded using the Medical Dictionary for Regulatory Activities (MedDRA; version in use by the Sponsor at the time of database lock).

Adverse events will be classified into predefined standard categories according to chronological criteria:

- Pre-treatment AEs: AEs that occurred, worsened, or became serious during the pre-treatment period.

- Treatment-emergent AEs: AEs that occurred, worsened, or became serious during the treatment emergent period.
- Post-treatment: AEs that occurred, worsened, or became serious during the post-treatment period.

Treatment-emergent AEs will be assigned to the dose level group actually received.

The following AEs summaries will be generated with number (%) of participants experiencing at least one event by dose level group for the safety population. Multiple occurrences of the same event in the same participant will be counted only once in the tables, using the maximum (worst) grade by treatment phase. Summaries will be provided for all grades combined and for Grade  $\geq 3$  (including Grade 5):

- Overview of TEAEs: number and percentage of participants with any TEAE, any Grade  $\geq 3$  TEAEs, any serious TEAE, any TEAE leading to death, any TEAE leading to permanent intervention discontinuation, any TEAE of special interest (AESI).
- Summary of TEAEs by primary SOC, high level group term, high level term, and preferred term: number and percentage of participants with at least one TEAE.
- Summary of TEAEs by primary SOC and PT: number and percentage of participants with at least one TEAE.
- TEAEs will also be described according to seriousness, maximum intensity (ie, grade), relation to the IMP and action taken.
- Number and percentage of participants experiencing treatment emergent AESI will be presented by AESI category and PT.
- Post-treatment AEs: overview, summary of AEs and serious AEs by primary SOC and PT.

All AEs reported in the study will be listed, sorted by participant and onset date. Participants presenting TEAEs will be listed sorted by primary SOC and PT. Any deaths, serious adverse events of special interest and other significant AEs, any AEs leading to permanent intervention discontinuation, will be listed.

#### 9.4.2.1.2 *Laboratory data*

For parameters with laboratory ranges and/or abnormality criteria (PCSA), analysis will be performed using all post-baseline assessments done during the TE period, including all unplanned and rechecked values. Counts of participants with PCSAs according to baseline status will be presented by dose level group. The same type of summary tables will be provided for out-of-normal laboratory range values.

Descriptive statistics of values and changes from baseline at each scheduled visit and graphs over time of key laboratory parameters will be provided for the intervention period and the follow-up period overall.

#### 9.4.2.1.3 *Vital signs and physical examinations*

For all parameters with PCSA definition, counts of participants with PCSAs will be presented by dose level group, regardless of the baseline status. All post-baseline assessments done during the TE period, including all unplanned and rechecked values, will be taken into account.

Descriptive statistics of vital signs, ie, heart rate (HR), systolic and diastolic blood pressures (SBP and DBP), will be provided by dose level group on the value and change from baseline at each scheduled visit for the intervention period and the follow-up period overall.

In addition, graphs over time may be provided for heart rate and blood pressures.

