## 9.4.2 Primary endpoint(s)

### 9.4.2.1 Part A

**Table 8 - Primary endpoint analysis for Part A**

Primary endpoint	Statistical analysis methods
Standard clinical and laboratory parameters and adverse events.	Descriptive summaries of Treatment-Emergent Adverse Events and Potentially clinically significant abnormalities.

All the safety analyses will be performed using the safety population from Part A, by dose level group.

The safety evaluation will be based upon the review of the individual values (clinically significant abnormalities), descriptive statistics (summary tables, figures) and, if needed, on statistical analysis (appropriate estimations, confidence intervals).

Potentially clinically significant abnormality (PCSA) values are defined as abnormal values considered medically important by the Sponsor, according to predefined criteria/thresholds based on literature reviews and defined by the Sponsor for clinical laboratory tests and vital signs (from sponsor's document BTD-009536 "Analysis and reporting of safety data from Clinical Trials through the Clinical Study Report", Appendix 3).

Adverse events will be graded according to the NCI-CTCAE v5.0 and related analyses will be provided by grades. For clinical laboratory evaluation, vital signs, and physical examination, analyses will be provided according to PCSA.

For all safety data, the following observation periods are defined and used for classification of AEs and determination of on-treatment PCSA values:

- The **pre-treatment period** is defined as the time between informed consent signature and the first IMP administration.
- The **treatment emergent (TE) period** is defined as the period from the first IMP administration up to 30 days after the last IMP administration.
- The **post-treatment period** is defined as the time starting after the TE period.

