1.2.2 Modification on '9.4.2.1.1 Adverse events'

An additional listing of all AEs will be generated. This detailed listing means the following protocol defined summaries and listings will not be presented:

- Treatment-emergent AEs (TEAEs) described according to seriousness, maximum intensity (ie, grade), relation to the investigational medicinal product (IMP) and action taken.
- Summary of post-treatment AEs.
- Participants presenting TEAEs listed sorted by primary system organ class (SOC) and preferred term (PT).

An additional summary of COVID19 related TEAEs will be generated by study intervention group with number (%) of participants experiencing at least one treatment emergent COVID19 related AE, sorted by the internationally agreed SOC order and decreasing frequency of PTs.

1.2.3 Modification on '9.4.2.1.2 Laboratory data' and '9.4.2.1.3 Vital signs and physical examinations'

In addition to the protocol defined outputs the following listings will be presented:

- Listing of participants with combined PCSAs for liver function – Safety population.
- Listing of laboratory data.
- Vital signs - Listing of participants with post-baseline abnormality (PCSA).

With the addition of the detailed listing of laboratory data noted above, which will include flags for PCSAs and abnormalities based on normal ranges, the protocol defined summary of out-of-normal laboratory range values will not be presented.

With the addition of the vital signs listing of participants with post-baseline abnormality (PCSA) noted above, the protocol defined descriptive statistics of vital signs will not be presented.

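### Part A vital-sign PCSA counts are not split by baseline status, and the SAP removes the change-from-baseline statistics that would have put them in context

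*Protocol*

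**What the plan says.** **Role of PCSAs.** Protocol Table 8 gives the Part A primary endpoint analysis as "Descriptive summaries of Treatment-Emergent Adverse Events and Potentially clinically significant abnormalities". Protocol 9.4.2.1 says that its observation periods are "used for classification of AEs and determination of on-treatment PCSA values". The treatment-emergent (TE) period "is defined as the period from the first IMP administration up to 30 days after the last IMP administration".

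**Laboratory rule (Protocol 9.4.2.1.2).** "Counts of participants with PCSAs according to baseline status will be presented by dose level group".

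**Vital-sign rule (Protocol 9.4.2.1.3).** "counts of participants with PCSAs will be presented by dose level group, regardless of the baseline status", and "All post-baseline assessments done during the TE period, including all unplanned and rechecked values, will be taken into account". The same section then promises descriptive statistics of heart rate and blood pressure by dose level group, as values and as changes from baseline. Graphs over time are optional.

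**SAP.** Section 1.1 keeps a PCSA analysis for vital signs. Section 1.2.3 adds a listing of participants with a post-baseline vital-sign PCSA and, because of that listing, states that "the protocol defined descriptive statistics of vital signs will not be presented". It does not alter the counting rule. Section 1.3 limits descriptive statistics and individual plots to hemoglobin and the hemolysis markers. For vital signs it again names only the PCSA listing.

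**The concern.** A safety count by dose group is more useful when the reader can see which abnormalities arose after dosing and which were already there. The other two by-group safety summaries offer this. A treatment-emergent adverse event must have begun, worsened or become serious in the TE period (Protocol 9.4.2.1.1), and laboratory PCSAs are shown against baseline status. The vital-sign count offers no such separation, and the protocol gives no reason for the difference.

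As the protocol stood, the gap was partly covered, because the changes from baseline were reported by dose group in the same section. Once the SAP removes them, nothing by group is left to show it. Part A has no control arm to give a background rate. Participants enter with hemoglobin below 10 g/dL (I 02) and may be on stable corticosteroids (E 17), so abnormal pre-dose vital signs are plausible, although the documents give no rate. Part B was not performed (SAP 1.2), so the Part A safety tables carry the only primary result that remains.

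**Working it through.** The plan states no figure on this point, so there is none to reproduce. The check is a comparison of the texts, followed by a calculation for scale.

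**1. What triggers a count.** Only post-baseline values within the TE period count, including unplanned and rechecked ones. A pre-dose value alone never does. A participant who was abnormal at baseline enters the count only if a later TE-period value also meets the PCSA limit. There are many chances for this: Protocol 8.2.2 schedules readings at 1, 2 and 4 hours after the Day 1 dose alone.

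**2. Which committed outputs separate new from persisting abnormality.**

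| Vital-sign output | Status after the SAP | Separates by baseline? |
|---|---|---|
| PCSA counts by dose group | Kept, rule unchanged | No |
| Values and changes from baseline by dose group | Dropped (SAP 1.2.3) | Would have given context |
| Graphs over time | Optional in the protocol; not in SAP 1.3 | Not committed |
| Listing of participants with a post-baseline PCSA | Added (SAP 1.2.3) | Columns not specified; not a by-group summary |

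SAP 1.2.3 says that the laboratory listing will carry flags for PCSAs and normal-range abnormalities. It says nothing comparable about baseline in the vital-sign listing.

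**3. Weight of one participant.** Cohorts are planned at 3 (Protocol 4.1), and Part A has at most 9 participants (Protocol 9.2.1).
- One cohort: 1/3 = 33.3 percentage points.
- All of Part A: 1/9 = 11.1 percentage points.

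**4. Illustration only.** Let p be the share of participants with a vital-sign PCSA at baseline, and q the chance that it is met again in the TE period. Neither is in the documents; both are assumed. If participants are independent, the chance that a group of n contains at least one such participant is 1 − (1 − pq)^n. For n = 3:
- p = 0.05, q = 0.5: 1 − 0.975³ = 0.073
- p = 0.10, q = 1: 1 − 0.90³ = 0.271
- p = 0.20, q = 1: 1 − 0.80³ = 0.488
- p = 0.30, q = 1: 1 − 0.70³ = 0.657

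Over p from 5% to 30% and q from 0.5 to 1, the range for n = 3 is 7.3% to 65.7%. For n = 9 it is 20.4% to 96.0%. Ranges this wide show that the situation could arise, not how often it would.

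**The case against.** The strongest reply is that the rule is openly stated, contradicts no other passage and drives no decision. There is no formal test (Protocol 9.1) and no sample size calculation for Part A (9.2.1). The dose-limiting toxicity rules in 10.1.9 use graded adverse events with attribution, not PCSA counts. Protocol 9.4.2.1 bases the safety evaluation partly on review of individual values, and with at most 9 participants each case can be examined. A clinically significant vital-sign abnormality can also be reported as an adverse event (10.3.1). All of this stands, and it is why the point is minor. Individual review settles a case easily only if baseline is visible beside the later value, and the SAP does not say that the listing will show it.

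The second reply is that the limits are not in front of us. Protocol 9.4.2.1 sets them "according to predefined criteria/thresholds based on literature reviews and defined by the Sponsor for clinical laboratory tests and vital signs", in a document that is not supplied. If a limit already requires a change from baseline, a stable pre-existing abnormality may never be counted. That also stands.

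A reader might go further and infer that a pre-dose abnormality is itself counted as an on-treatment one, or that the count is shown to be biased upward as a measure of drug effect. The documents support neither. The later value must meet the limit again, and it is then truly an on-treatment value, though not necessarily a new finding. The plan uses on-treatment as a label for timing and nowhere offers the count as an estimate of drug effect. Nor can the presence or size of any bias be established without the criteria and a baseline rate.

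**Conclusion.** The point holds as a limit on what the committed tables can show. After SAP 1.2.3, no by-group vital-sign output that the plan commits to distinguishes a persisting pre-dose PCSA from a new one, whereas the laboratory PCSA table does. One such participant is a third of a planned cohort. The consequence falls on the reading of the final Part A safety table, not on any test or dosing rule.

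The conclusion assumes that at least one vital-sign PCSA limit can be met by an unchanged value, and that some participants meet it before dosing. Neither can be confirmed from the documents. The severity is minor; the change is worth making because it costs little.

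**What to change.** Edit SAP 1.2.3 only:
- Present vital-sign PCSA counts by dose level group and by baseline PCSA status, as for laboratory data, taking baseline as SAP 1.3 defines it (the last value before administration).
- Keep the all-participants count as a total row, so that the protocol's table is still delivered.
- Show the baseline value and baseline PCSA status in the planned vital-sign PCSA listing.
- Where a PCSA limit contains a change-from-baseline condition, say in a footnote how baseline status was assigned.

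The cost is a few lines of SAP text, one split in an existing table and two listing columns. Pre-dose vital signs are already taken on Day 1 (Protocol 8.2.2), so no new data are needed. SAP 1.2 already records departures from the protocol's statistical section, so the change can be entered there without editing the protocol.

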#### 9.4.2.2 *Part B*

**Table 9 - Primary endpoint analysis for Part B**

Primary endpoint	Statistical analysis methods
Overall response rate (response (R) or complete response (CR)) at Day 85: 

• R is defined as an increase in hemoglobin by <math>\geq 2</math> g/dL from baseline and an absence of transfusion in the last 7 days and absence of rescue medications in the past 4 weeks, without biochemical resolution of hemolysis.

• CR is defined as hemoglobin <math>\geq 11</math> g/dL (women) or <math>\geq 12</math> g/dL (men), no evidence of hemolysis (normal bilirubin, LDH, haptoglobin, and reticulocytes), and absence of transfusion in the last 7 days and absence of rescue medication in the past 4 weeks

	The proportion of overall response will be computed at Day 85 together with its exact 95% confidence interval using Clopper-Pearson method. Participants whose response at Day 85 is not evaluable, whatever the reason (eg, early discontinuation), will be considered as non-responders.

The primary analysis will be conducted in the efficacy population, which will be used as the denominator for computation of the response rate.

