Part A (Cohorts 2 and 3 only)	

• To evaluate the efficacy of isatuximab in adults with wAIHA.

• Overall response rate (response (R) or complete response (CR)) at Day 85.

R is defined as an increase in hemoglobin by <math>\geq 2</math> g/dL from baseline and an absence of transfusion in the last 7 days and absence of rescue medications in the past 4 weeks. Biochemical evidence of hemolysis may still be present.

CR is defined as hemoglobin <math>\geq 11</math> g/dL (women) or <math>\geq 12</math> g/dL (men), no evidence of hemolysis (normal bilirubin, LDH, haptoglobin, and reticulocytes), and absence of transfusion in the last 7 days and absence of rescue medication in the past 4 weeks.

• Proportion of participants with durable hemoglobin response by Day 169. Durable response is defined as Hb level <math>\geq 10</math> g/dL with an increase from baseline of <math>\geq 2</math> g/dL on three consecutive evaluable visits during the study period; with absence of transfusion and no rescue medication during the period of 3 consecutive visits and for at least 7 days (transfusions) and 4 weeks (rescue medication) prior to the first consecutive visit.

• Overall response rate at Day 169, median time to R or CR, median time to loss of R or CR (loss of R defined as hemoglobin <math>< 10</math> g/dL at two consecutive visits at least 7 days apart and initiation of new treatment for anemia or increase in steroid dose; loss of CR is defined as hemoglobin <math>< 11</math> g/dL (women) or <math>< 12</math> g/dL (men) at two consecutive visits at least 7 days apart), proportion of participants requiring rescue therapy (any wAIHA-directed therapy other than prednisone or transfusion) or splenectomy.

Objectives	Endpoints

 
To evaluate the impact of isatuximab treatment on fatigue.
 
 
Part B
 
 
To evaluate the safety and tolerability of isatuximab in adults with wAIHA.
 
To evaluate the durability of response to isatuximab and time to response.
 
	
 
FACIT-fatigue scale score at Day 85 and Day 169.
 

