### **9.4.3 Secondary endpoint(s)**

#### **9.4.3.1 Part A (Cohorts 2 and 3 only)**

##### **9.4.3.1.1 Analysis of efficacy**

The following analysis of clinical response and fatigue will be conducted in the efficacy population of Part A for Cohorts 2 and 3 only. Response data will be listed for participants from all cohorts.

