#### **Overall response rate at Day 85**

The overall response rate (including the breakdown for complete response and response) will be described by dose level group at each visit of the intervention period including Day 85 and using the same approach for participants with a non-evaluable response as in [Section 9.4.2.2](#).

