#### **Time to response and durability of response**

The proportion of participants with durable hemoglobin response by Day 169 will be computed together with its exact 95% confidence interval.

The proportion of overall response will be computed at Day 169. Participants whose response at Day 169 is not evaluable, whatever the reason (eg, early discontinuation), will be considered as non-responders.

The overall response rate (including the breakdown for complete response and response) will be described by dose level group at each visit of the follow-up period.

The time to response (CR or R) will be computed as the time between the start of treatment until the first documented response (in days) and described by summary statistics (using n, mean, standard deviation, interquartile range, median, minimum, and maximum)

The time to loss of response (in days) will be computed as the time between the first documented response (CR or R) and the first documented loss of response (ie, neither R nor CR as detailed in [Section 3](#)) and described by summary statistics (using n, mean, standard deviation, interquartile range, median, minimum, and maximum). For participants still showing a response at the end of the follow-up period, the end date will be the last date where the response is assessed.

Depending on the number of responses, the time to response and the time to loss of response will be listed or described by dose level group in the subset of participants who achieved a response during the intervention period as well as in the subset of participants who achieved a response during the study including the follow-up period (if different).

The time to loss of CR (in days) will be computed as the time between the first documented CR and the first documented loss of CR (as detailed in [Section 3](#)) and described by summary statistics (using n, mean, standard deviation, interquartile range, median, minimum, and maximum). For participants still showing a CR at the end of the follow-up period, the end date will be the last date where the response is assessed.

Depending on the number of CRs, the time to loss of CR will be listed or described by dose level group in the subset of participants who achieved a CR during the intervention period as well as in the subset of participants who achieved a CR during the study including the follow-up period (if different).

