### **Time to response and durability of response**

The proportion of overall response at Day 169 and its exact 95% confidence interval using Clopper-Pearson method, the time to response and durability of response, and the proportion of participants requiring rescue therapy or splenectomy will be summarized, using the same approach and definitions as in [Section 9.4.3.1.1](#).

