1 STATISTICAL AND ANALYTICAL PROCEDURES

1.1 INTRODUCTION

The purpose of this document is to provide additional technical details.

A comprehensive and detailed description of strategy and statistical technique used to perform the analysis of data was provided in Section 9 of the protocol (Amended Clinical Trial Protocol, Version 06, dated 28-Mar-2022).

Modifications from analyses specified in the protocol are defined in [Section 1.2](#).

Details for analyses defined in the protocol and additional analyses are further specified in [Section 1.3](#).

Adverse events (AEs) will be coded according to the Medical Dictionary for Regulatory Activities (MedDRA version currently in effect at the time of database lock, version 26.0 or later).

Previous and concomitant medication records will be coded according to the World Health Organization Drug Dictionary (WHO-DD version currently in effect at the time of database lock, version 2023MAR B3 or later).

For laboratory variables, analyses according to National Cancer Institute (NCI) grading will be made according to the NCI common terminology criteria for AEs (CTCAE) version currently in effect at the time of database lock. In addition, for laboratory variables for which NCI-CTCAE scale is not applicable, and vital sign variables, potentially clinically significant abnormality (PCSA) analyses will be performed based on the PCSA list from BTD-0090536 version 3.0 dated May 2014 (“Analysis and reporting of safety data from Clinical Trials through the Clinical Study Report”, Appendix 3).

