1.2 MODIFICATIONS FROM THE STATISTICAL SECTION OF THE PROTOCOL

This study stopped early and, as a result, Part B was not performed. Therefore, all protocol defined analyses planned for Part B will not be presented.

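### Does the wording of response (R) in protocol Table 9 put the Part A response rates at risk of misclassification?

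*Protocol*

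**What the plan says.** R appears in three parts of the protocol. The Synopsis and Section 3 (Table 2) define it, for both the Part B primary endpoint and the Part A secondary endpoint in Cohorts 2 and 3, as a hemoglobin rise of at least 2 g/dL with no transfusion in the last 7 days and no rescue medication in the past 4 weeks. They add "Biochemical evidence of hemolysis may still be present". Table 9 in Section 9.4.2.2 (Part B) has the same hemoglobin, transfusion and rescue terms but ends "absence of rescue medications in the past 4 weeks, without biochemical resolution of hemolysis". CR is the same throughout: hemoglobin of at least 11 g/dL (women) or 12 g/dL (men), normal bilirubin, LDH, haptoglobin and reticulocytes, and the same transfusion and rescue conditions.

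The Part A analysis text (Section 9.4.3.1.1) does not restate R. For the Day 85 rate it refers to Section 9.4.2.2 by "using the same approach for participants with a non-evaluable response as in". For loss of response it refers to Section 3 by "ie, neither R nor CR as detailed in". It also promises that "Response data will be listed for participants from all cohorts".

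SAP Section 1.1 says that the "description of strategy and statistical technique used to perform the analysis of data was provided in Section 9 of the protocol", and that departures from the protocol are in SAP Section 1.2. That section opens with "This study stopped early and, as a result, Part B was not performed" and drops the Part B analyses. No item in it alters R or CR.

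**The concern.** The Section 3 wording permits persisting hemolysis, whereas the Table 9 wording can be read as requiring it. The literal reading leaves a hole between R and CR. A participant whose markers normalise before hemoglobin reaches the CR cut-off falls into it, while the same participant with abnormal markers counts as R.

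There is also a route by which this could reach the output. The SAP text supplied defines neither R nor CR and refers to protocol Section 9 for methods, where Table 9 is the only place R is spelled out. SAP Section 1.2.1 still speaks of a primary efficacy endpoint, although the primary endpoint of Part A is safety. With Part B gone, the response rates in the 280 mg x6 and 560 mg x6 groups are among the main efficacy results left. If a programmer built one R flag from Table 9 and used it for Part A, the visit-level response rates and time to response would inherit it.

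**Working it through.** **The plan's own figure.** The only sizing figure for this endpoint is Table 6. For 7 of 14, the Clopper-Pearson limits are the 0.025 quantile of Beta(7, 8) and the 0.975 quantile of Beta(8, 7), that is 0.2304 and 0.7696. The half-width is (0.7696 - 0.2304)/2 = 0.2696, against 0.230, 0.770 and 0.270 in the table. It reproduces, and it does not depend on how R is worded.

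**Where the wordings differ.** Take the transfusion and rescue conditions as met.

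| Rise of at least 2 g/dL | Hemoglobin at CR cut-off | All markers normal | Section 3 | Table 9, literal |
|---|---|---|---|---|
| no | no | no | none | none |
| no | no | yes | none | none |
| no | yes | no | none | none |
| no | yes | yes | CR | CR |
| yes | no | no | R | R |
| yes | no | yes | **R** | **none** |
| yes | yes | no | R | R |
| yes | yes | yes | CR | CR |

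One row of eight differs. If the Table 9 phrase is read as *even without resolution*, no row differs.

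**Width of the hole under the literal reading.** It runs from baseline b + 2 up to the CR cut-off: max(0, 12 - (b + 2)) for men and max(0, 11 - (b + 2)) for women.

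| Baseline (g/dL) | Men | Women |
|---|---|---|
| 7.0 | 3.0 | 2.0 |
| 8.0 | 2.0 | 1.0 |
| 8.5 | 1.5 | 0.5 |
| 9.0 | 1.0 | 0 |
| 9.5 | 0.5 | 0 |

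Inclusion criterion I 02 requires hemoglobin below 10 g/dL at screening. If that also holds at baseline, the hole can be reached by any man and by women starting below 9 g/dL.

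**Is the literal reading credible?** Take a man with a baseline of 8.0 g/dL. At 11.5 g/dL with abnormal markers he is R. If his markers then normalise, the literal reading makes him a non-responder. At 12.0 g/dL he becomes CR. A response scale that drops a patient as he improves towards CR is unlikely to be intended; the phrase makes sense as separating R from CR.

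**Size if the error were made.** One reclassified participant moves the rate by 100/n points: 33.3 at n = 3 and 16.7 at n = 6 (both cohorts pooled). At n = 3 the exact 95% limits, shown for scale because the plan gives no interval for the Part A Day 85 rate, are:

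| Responders | Rate | Limits |
|---|---|---|
| 0/3 | 0% | 0 to 70.8% |
| 1/3 | 33.3% | 0.8 to 90.6% |
| 2/3 | 66.7% | 9.4 to 99.2% |
| 3/3 | 100% | 29.2 to 100% |

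A fall from 2/3 to 1/3 is large as a percentage but well inside either interval.

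**Which definition governs each remaining output.**
- Part A response by visit, including Day 85: the endpoint is defined in Section 3 under Part A (Cohorts 2 and 3). The link to Section 9.4.2.2 covers non-evaluable responses only.
- Part A loss of response: Section 3, by explicit reference.
- Part A durable response: hemoglobin, transfusion and rescue only, so the markers play no part.
- Part B Day 85, the one analysis Table 9 covers: not presented.
- Part B Day 169: also not presented, and it took its rules from Section 9.4.3.1.1 ("using the same approach and definitions as in"), not from Table 9.

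**The case for a change.** The best case for acting is that the SAP is the document programmers work from. It sends them to protocol Section 9, and the one wording of R they find there is the ambiguous one. The explicit Section 3 reference in the Part A text is attached to loss of response, so no sentence in the analysis text itself says which wording governs the Part A Day 85 rate. With 3 participants per group one slip moves a rate by a third, and a clarifying sentence costs almost nothing.

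What stands is that the two wordings differ, that the SAP text supplied does not restate R or CR, and that the literal reading would misclassify. What does not stand is that the plan leads there. The SAP refers to Section 9 for strategy and technique, and describes itself as adding technical detail; endpoint definitions remain in the protocol unless SAP Section 1.2 changes them, and it does not. The mention of a primary efficacy endpoint in SAP Section 1.2.1 settles only local versus central laboratory source, and protocol Section 8.1 uses that term for overall response rate without naming Part B. To go wrong, an analyst would have to pass over the definition written for Part A and apply a table headed Part B. Even then, response data are listed for all cohorts and SAP Section 1.2.3 adds a listing of laboratory data, so the error would be visible in a handful of participants.

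**Conclusion.** No change is called for. The phrase in Table 9 is a clerical inconsistency in the analysis of a part that was not run. Followed as written, the plan classifies Part A by Section 3, so no result still to be reported changes. A SAP sentence saying so would be optional, and the Table 9 phrase need be aligned with Section 3 only if the protocol text is reused.

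The 33.3-point step is what one participant would cost if Table 9 were both read literally and carried over to Part A, and the plan directs neither. The documents do not say how many participants would fall in the affected category; it may be none. No formal test is planned and the Part A Day 85 rates are only described, so no inference hangs on the point.

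This rests on three assumptions: cohort sizes are the planned 3, since the SAP text gives no actual numbers; baseline hemoglobin is below 10 g/dL, as required at screening; and the SAP pages removed from the copy supplied do not redefine R or CR.
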